#### 2. OBJECTIVES

The utility and efficacy of ranibizumab in eyes with DME that are naïve to VEGF inhibitors has been shown in the RISE/RIDE trials and others. However, many eyes have been previously treated (recent and frequent) with other VEGF inhibitors (in particular, bevacizumab). Our primary objective is to understand the functional and anatomic effectiveness of ranibizumab following previous anti-VEGF. Additionally, the optimal dosing regimen remains to be determined. Monthly dosing was evaluated in the RISE/RIDE trials, but monthly dosing may not be necessary or practical in all patients. This study will also compare a "treat-and-extend" dosing regimen to a monthly dosing regimen.

#### 2.1 Primary Objective

The primary objective of the study is to assess the ocular and systemic adverse events of ranibizumab for DME following previous treatment with intravitreal bevacizumab (worsened acuity >30 letters, retinal detachment, endophthalmitis, cataract progression, vitreous hemorrhage, new PDR or neovascularization of the iris or angle, systemic thromboembolic events, deaths and systemic serious adverse events).

#### 2.2 Secondary Objectives

The secondary objectives include:

- mean change from baseline in best-corrected visual acuity at months 6 and 12
- mean absolute change from baseline central foveal thickness at months 6 and 12 as measured by SDOCT (defined as the average thickness within the central 1 mm subfield)
- proportion of subjects that were anatomically "dry" by SDOCT at months 6 and 12
- proportion of participants who gained greater than or equal to 15 letters of vision at months 6 and 12
- proportion of participants who lost greater than or equal to 15 letters of vision at months 6 and 12
- proportion of patients that are 20/40 or better at months 6 and 12
- comparison of extent of angiography leakage from baseline to months 3, 6, and 12,
- comparison of peripheral nonperfusion from baseline to months 3, 6 and 12
- total number of injections

- Assessment of pre-trial anatomic improvement based on OCT on bevacizumab prior to switching to ranibizumab. Analysis will also be stratified based on subsequent response to ranibizumab.
- Assessment of pre-trial functional improvement based on snellen visual acuity prior to switching to ranibizumab. Analysis will also be stratified based on subsequent response to ranibizumab.

# 3. STUDY DESIGN

# 3.1 DESCRIPTION OF THE STUDY

This is an open-label, Phase I/II study of intravitreally administered 0.3mg ranibizumab in subjects with DME previously treated with intravitreal bevacizumab with a randomized comparative dosing strategy (monthly vs "treat-and-extend"). Thirty patients total will be enrolled in the study, 15 in each group. This study will have a 1-year treatment period. The recruitment period will occur over 1 year with a total potential study duration of 2 years. Interim analysis performed at 6 months and final analysis at 1 year.

Group 1 (monthly group) n=15

Consented, enrolled subjects will receive multiple open-label intravitreal injections of 0.3 mg ranibizumab administered every 30 days (+/- 7 days from the last treatment) for 12 months in the monthly group.

Group 2 ("treat-and-extend" group) n=15

 In the "treat-and-extend" group, eyes will be treated with 3 loading doses at 30-day intervals (+/- 7 days from the last treatment). After the third loading dose, the follow-up interval is determined with an OCT-based protocol.

Angiography assessment:

Both qualititative and quantitative assessment of angiographic features will be performed on obtained angiograms. This will include evaluation of leakage, microaneurysms and ischemia. This is detailed in Appendix D. Addendum for

Prior anti-VEGF response assessment:

Utilizing available clinical and imaging data contained in the medical record, assessment of functional (visual acuity) and anatomic (OCT) responses will be assessed. This information would be assessed in detail following review of this data for appropriate inclusion/exclusion parameters for the study. This is detailed in Appendix E.

## 3.2 RATIONALE FOR STUDY DESIGN

RISE/RIDE have shown that ranibizumab is an effective treatment for DME in anti-VEGF naïve eyes. However, many patients have been previously treated with bevacizumab or are initially started on bevacizumab. The efficacy and safety of ranibizumab following previous bevacizumab therapy is unknown. In addition to better understanding the role for ranibizumab following bevacizumab, this study also aims to evaluate a dosing regimen that reduces treatment/visit burden. Diabetes is a chronic disease and often these patients are younger than the age-related macular degeneration population. The burden of monthly visits and cumulative risk of monthly treatment over years should not be ignored and is likely not practical. This study will evaluate one of the most popular anti-VEGF treatment regimens for neovascular agerelated macular degeneration: "treat-and-extend." This novel approach minimizes visits and treatment while maximizing the anatomic results [minimizing the cycle of edema recurrence that triggers therapy in a pro re nata (PRN) regimen].

Addendum for Quantitative Assessment of Ultra-Widefield Angiographic Features in Diabetic Macular Edema

Objective and quantitative assessment of angiographic imaging is currently lacking. Subjective interpretation of angiographic patterns and features limit the analysis and potential of utilizing the modality as a true biomarker of diagnostic and therapeutic value. The complex patterns noted within angiography, including staining, leakage, pooling, blockage, nonperfusion, and window defects are amenable to quantatitive assessment and integrative analysis for pattern recognition. This complex pattern analysis could be utilized to create an activity fingerprint that may have value in therapeutic assessment and monitoring.

Common angiographic features in DME in these conditions include vascular staining/leakage, microaneurysms, capillary nonperfusion, and neovascularization. Differential response to anti-VEGF therapy is quite

frequent among patients, vascular patterns and angiographic features may provide important insight into the optimal therapeutic or reason for lack of response. The ability to objectively characterize the patterns and features of the angiographic features would be an important advance in characterizing retinal vascular conditions.

# 3.3 OUTCOME MEASURES

#### 3.3.1 Primary Outcome Measures

The primary outcome measures for safety and tolerability are the following:

- Incidence and severity of ocular adverse events, as identified by eye examination (including visual acuity testing)
- Incidence and severity of other non-ocular adverse events, as identified by physical examination, subject reporting, and changes in vital signs

# 3.3.2 Secondary Outcome Measures

- Mean change in best-corrected visual acuity as assessed by the number of letters read correctly on the electronic ETDRS eye chart from baseline to months 6 and 12.
- Mean absolute change from baseline central foveal thickness at months 6 and 12 as measured by SDOCT (defined as the average thickness within the central 1 mm subfield)
- Proportion of eyes that were anatomically "dry" by SDOCT at months 6 and 12.
- Proportion of eyes gaining greater than or equal to 15 letters of vision at months 6 and 12.
- Proportion of eyes losing greater than or equal to 15 letters of vision at months 6 and 12.
- Proportion eyes with 20/40 or better best-corrected visual acuity at months 6 and 12.
- Comparison of extent of angiographic leakage from baseline to months 3, 6 and 12.
- Comparison of extent of peripheral nonperfusion from baseline to months 3, 6, and 12.
- Comparison of previous anatomic anti-VEGF response to month 3, month 6, and month 12 anatomic response.

• Comparison of previous functional anti-VEGF response to month 3, month 6 and month 12 functional response

# 3.4 SAFETY PLAN

The safety assessments to be conducted for this study are listed in Section 4.5 and Appendix A.

Potential ocular adverse events associated with intravitreal injections include ocular irritation, subconjunctival hemorrhage, corneal abrasion, floaters, vitreous hemorrhage, retinal tear, retinal detachment, endophthalmitis, lens damage, and intraocular inflammation. The risk of severe ocular side effects (e.g., endophthalmitis, retinal detachment) is approximately 1/1000. Potential theoretical systemic adverse events include stroke and myocardial infarction. However, patients with diabetes are also at higher risk of stroke and myocardial infarction. The incidence of these serious side effects were 2.4 to 8.8% in the ranibizumab group compared to 4.9 to 5.5% in the sham group in the RISE/RIDE studies.

Given the rarity of these events, this study will not be powered to discern significant differences between the two comparison groups in the incidence in severe adverse events. As in any study, conclusions regarding the incidence of rare adverse events will not be able to be definitively determined in this study.

All adverse events will be reported to by the investigator and/or designee to the principal investigator and to the IRB.

# 3.5 COMPLIANCE WITH LAWS AND REGULATIONS

This study will be conducted in accordance with current U.S. Food and Drug Administration (FDA) Good Clinical Practices (GCPs), and local ethical and legal requirements.

# 4. MATERIALS AND METHODS

# 4.1 SUBJECTS

#### 4.1.1 Subject Selection

**30** subjects from approximately **1** site in the United States will be enrolled. Subjects will be recruited through clinics at the Cole Eye Institute, Cleveland OH. Eligible subjects will be administered and provided with a copy of informed consent. (See Appendix *A*, the study flow chart, for screening assessments). Fellow eyes that develop DME during the study period or have DME at study entry will be treated with ranibizumab at investigator discretion. Genentech will supply drug for the nonstudy eye. In the event that both eyes are eligible at study entry, the eye with more significant macular edema as defined by the central foveal thickness will be the study eye.

# 4.1.2 Inclusion Criteria

Subjects will be eligible if the following criteria are met:

- Ability to provide written informed consent and comply with study assessments for the full duration of the study
- Age > 18 years
- ETDRS best-corrected visual acuity of 20/25 to 20/320 in the study eye
- Willing, committed, and able to return for ALL clinic visits and complete all study related procedures
- At least 6 previous bevacizumab injections for diabetic macular edema in the last 12 months.
- At least 2 bevacizumab injections within 10 weeks and the most recent bevacizumab injection within 6 weeks of baseline study visits
- Persistent foveal-involving diabetic macular edema based on presence of intraretinal and/or subretinal fluid by SDOCT in the foveal center at study entry

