#### 1.3 RANIBIZUMAB AND DIABETIC MACULAR EDEMA

As noted above, the pivotal RISE/RIDE phase III trials resulted in the FDA approval of ranibizumab for the treatment of DME. Numerous trials have suggested the efficacy and safety of ranibizumab in the treatment of DME, including the DRCR.net, READ, and RISE/RIDE. The results of these studies suggest that intravitreal ranibizumab therapy is a safe and effective

treatment modality for DME. Ranibizumab therapy results in functional stabilization in the vast majority of eyes and in significant improvement in nearly half of eyes. Additionally, RISE/RIDE revealed that eyes treated with ranibizumab had lower rates of retinopathy progression and higher rates of retinopathy improvement. In addition to the functional improvements, ranibizumab resulted in significant anatomic improvements with a mean reduction of ~ 250 microns in central foveal thickness compared to only 133 micron decrease in the laser group.

Prior to the approval of ranibizumab, bevacizumab was the only readily available VEGF inhibitor being utilized (off-label) for the treatment of DME. Although the functional results to bevacizumab therapy, appear promising, the systemic safety of bevacizumab for DME and the relative efficacy of bevacizumab compared to ranibizumab remain unknown. With ranibizumab's approval, it is unclear whether switching from bevacizumab to ranibizumab has a clinical impact on the disease course. Given the number of eyes treated with bevacizumab, answering this question is important. These questions are the focus of this investigation.

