#### b. Administration

Group 1 will undergo monthly intravitreal injections of 0.3 mg ranibizumab administered 30 days (+/- 7 days) following the last treatment for 12 months. Injections will be performed with sterile technique as outlined in appendix B.

Group 2 will be assigned to a "treat-and-extend" protocol. Eyes will be treated with 3 loading doses at 30-day (+/- 7 days) intervals. After the third loading dose, the follow-up interval is determined with an OCT-based protocol:

• **Criterion A:** If the central subfield thickness is less than or equal to 300 microns or there is complete absence of intraretinal or

subretinal fluid on the macular cube, the follow-up interval is increased by 2 weeks (+/- 7 days) at each visit [to a maximum interval of 12 weeks (+/- 7 days)]. The eye receives an intravitreal ranibizumab injection at every visit.

- Criterion B: If on subsequent follow-up visits, the thickness increases above 300 microns or there is recurrence of fluid with thickness above 300 microns, the interval is reduced by 2 weeks (+/-7 days) (to a minimum interval of 4 weeks). Designated visits will also occur at 6 months and 12 months for visual acuity, ocular examination, FA, and OCT. No treatment will occur at these visits unless the time coincides with the scheduled "treat-and-extend" visit.
- Criterion C: Rescue criteria If on subsequent follow-up visits, a
  patient loses > 15 letters with associated recurrence of fluid or
  central subfield thickness above 300 microns, the dosing interval will
  be immediately reduced to 4 weeks (+/- 7 days) for the next followup visit and for the residual duration of the study.

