# Group 1 (Monthly treatment group): Month 1-Month 11 (+/- 7 Days)

The following information will be collected:

- Concomitant medications
- AEs

- ETDRS visual acuity with manifest refraction
- Slit lamp examination
- Fundus examination
- Spectral Domain OCT evaluation

- Intravitreal injection of ranibizumab
- Ultra-widefield fluorescein angiogram (months 3 and 6)
- Pulse and blood pressure

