#### Appendix E: Pre-Ranibizumab Assessment of Anti-VEGF Therapeutic Response.

 As part of the screening process for REACT, the medical records are reviewed for prior treatment, medical history, and ophthalmic history information for assessment of inclusion and exclusion criteria. The same medical record will be reviewed for specific data on functional (visual acuity) and anatomic (OCT) data on response to bevacizumab prior to exposure to ranibizumab in the trial. This will be performed in a retrospective fashion without any additional contact with study subjects or study interventions. Overall response to therapy as well as stratification to ranibizumab response will be assessed (e.g., dramatic responder vs nonresponder). Subjects would also be evaluated in the context of their bevacizumab response (nonresponder vs incomplete responder vs tachyphylaxis).

•

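### The before-after change on ranibizumab combines a change of drug with a change of injection frequency, and no planned analysis uses prior bevacizumab frequency

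*Protocol*

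**What the plan says.** Three entry criteria in Protocol 4.1.2 bear on this point. The first sets the yearly minimum: "At least 6 previous bevacizumab injections for diabetic macular edema in the last 12 months". The second concerns recent treatment: "At least 2 bevacizumab injections within 10 weeks and the most recent bevacizumab injection within 6 weeks of baseline study visits". The third requires remaining fluid: "Persistent foveal-involving diabetic macular edema based on presence of intraretinal and/or subretinal fluid by SDOCT in the foveal center at study entry".

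Protocol 4.3.2b then sets the on-study schedule. For the monthly arm, "Group 1 will undergo monthly intravitreal injections of 0.3 mg ranibizumab administered 30 days (+/- 7 days) following the last treatment for 12 months". Section 4.5.1 and the Appendix A flowchart place these injections at Months 0 to 11, with none at Month 12. Group 2 has three loading doses 30 days apart. After that the interval lengthens by 2 weeks per visit, to at most 12 weeks, while the OCT criteria are met.

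Protocol 1.3 makes the effect of changing drug a focus of the trial: "it is unclear whether switching from bevacizumab to ranibizumab has a clinical impact on the disease course". Sections 3.3.2 and 4.8.3 compare the previous anti-VEGF response with the response at months 3, 6 and 12. For the pre-trial period, Appendix E states: "The same medical record will be reviewed for specific data on functional (visual acuity) and anatomic (OCT) data on response to bevacizumab". It then classes eyes as nonresponder, incomplete responder or tachyphylaxis. The SAP gives paired t-tests from start to end, unpaired t-tests between regimens and a chi-squared test for ophthalmic adverse events. It names no covariate, stratum or subgroup. Section 2.2 lists the total number of injections as a secondary objective but does not link it to the pre-trial count.

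**The concern.** Fluid at entry can persist for two different reasons: the eye was injected often and bevacizumab did not clear it, or the eye was injected at long intervals. Both kinds of eye meet the criteria. On study, every eye gets three monthly doses, and Group 1 stays monthly. An eye of the second kind could improve because it is now injected more often, whatever the drug.

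The paired t-test cannot tell these cases apart. Nor can the comparison of previous with on-study response, because the previous response was obtained on a schedule that the analysis does not record. The labels in Appendix E describe the bevacizumab period only, but they are hard to read without knowing how often the eye was then injected. At stake is the wording of the conclusion: a gain reported as the result of switching drug may partly be the result of a denser schedule.

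**Working it through.** The plan states no figure for the change in frequency, so there is none to reproduce. The check is a count.

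**Group 1.** Injections at Months 0 to 11 make 12. Ratio = 12 / prior count. The documents do not give the prior counts of enrolled eyes, so a range of 6 to 12 is assumed.

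| Prior injections in 12 months | Ratio in Group 1 |
|---|---|
| 6 | 12/6 = 2.0 |
| 8 | 12/8 = 1.5 |
| 10 | 12/10 = 1.2 |
| 12 | 12/12 = 1.0 |

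**Group 2, prior count 6.** With the fastest extension and a first post-loading interval of 6 weeks, injections fall on days 0, 30, 60, 102, 158, 228 and 312. That is 7 injections, and 7/6 = 1.17. If the first post-loading interval is still 30 days, they fall on days 0, 30, 60, 90, 134, 192, 264 and 348. That is 8, and 8/6 = 1.33. With no extension there are 12, and 12/6 = 2.0. The range is about 1.2 to 2.0.

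**Recency criterion, read as 10 weeks before baseline.**
- At the minimum there are 2 injections in 70 days, a mean of 70/2 = 35 days per injection. Against 30 days on study the ratio is 35/30 = 1.17.
- The mean interval at the yearly minimum is 365/6 = 60.8 days (8.7 weeks). A steady schedule this sparse passes only if the last injection was at most 70 − 60.8 = 9.2 days before baseline. Injections on days −310, −249, −188, −127, −66 and −5 would pass.
- If the last injection was 28 days before baseline (an assumption, since no minimum gap is stated), a steady interval can be at most 70 − 28 = 42 days. That gives about 365/42 = 8.7, or 9 injections, and a Group 1 ratio of 12/9 = 1.33.
- An eye at both minimums had its other 6 − 2 = 4 injections in the earlier 52 − 10 = 42 weeks, or one per 42/4 = 10.5 weeks.

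**What an adjustment could show.** By the Fisher approximation (two-sided 0.05, 80% power), the smallest detectable correlation between prior frequency and change is tanh[(1.96 + 0.84)/√(n − 3)]. This is about 0.49 for n = 30 and 0.67 for one arm of 15.

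**The case against.** The strongest reply is the recency criterion. A reader who sees only the yearly minimum might infer that injection frequency doubles at entry. The documents do not support that for recent treatment: the average increase over the last 10 weeks is about 1.17 times at the minimum, and steady dosing every 8 to 9 weeks is an edge case. An eye with only 6 injections in the year would usually have been on a closer schedule before Day 0, so its baseline already reflects part of the change. This stands, and it limits the effect on the paired change. It does not remove it. The criterion does not fix the spacing of the last two injections, and it leaves the earlier 42 weeks open, where much of the bevacizumab response is judged.

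A reader might also infer that three injections in each eye would qualify, because the bevacizumab criteria do not name the study eye. Section 4.1.1 judges eligibility eye by eye, so that reading is strained.

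A third tempting step is to take the switching conclusion from eyes whose prior interval matched their on-study interval. In Group 2 the on-study interval is set by OCT response after baseline, so matching on it would select eyes by outcome. Prior frequency was not randomised either, and may follow disease severity. With no arm continuing bevacizumab, adjustment can describe the mixture but cannot separate its parts.

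It is also fair to say that this is a pilot of 30 with a safety primary objective, and that Appendix E already has prior treatment reviewed for eligibility. What is missing is the use of that history in the analysis.

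**Conclusion.** The point holds for the secondary before-after analyses and for the comparison of previous with on-study response. Over 12 months, injection frequency changes by a factor of 1.0 to 2.0 in Group 1 for prior counts of 12 down to 6, and by about 1.2 to 2.0 for a Group 2 eye at the minimum. Over the last 10 weeks the average factor at the minimum is about 1.17. How much acuity or thickness change this produces cannot be computed from the documents.

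One might infer that the trial's main results are compromised, but they are not. The randomised comparison of monthly with treat-and-extend dosing is unaffected, apart from chance imbalance with 15 per arm, and so is the primary safety endpoint. The result rests on three assumptions: prior counts of 6 to 12, the recency criterion read as counting back from baseline, and injections given as the flowchart lists them. This is a cheap improvement that changes what the trial can conclude about switching.

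**What to change.** 1. In Appendix E, add the number and dates of study-eye bevacizumab injections in the prior 12 months and in the last 10 weeks. Report the bevacizumab-response labels alongside them.
2. In the SAP, add a descriptive table of change in best-corrected visual acuity and central subfield thickness, with confidence intervals, by prior injection count or mean prior interval. Both are baseline variables. Do not match on the on-study interval. The documents suggest no cut-point, so any grouping should be fixed before the data are seen.
3. State in the protocol and SAP that the before-after change is the combined effect of drug and schedule and is not attributed to the change of drug alone.

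Naming the study eye in the two bevacizumab criteria would also help, but only as a drafting clarification.

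The cost is one or two chart-review fields, taken from records already reviewed for eligibility, and one table. Sample size, visits and treatment stay as they are. The drawback is precision: at n = 30 the intervals will be wide, so the table is descriptive and should carry no test-based claim.
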